Study Center(s)	Multi-center; 10 sites total
Number of Subjects	60
Diagnosis and Main Inclusion Criteria	History of chronic oral food refusal and be primarily fed through a G or G-J tube
Study Product, Dose, Route, Regimen	Megestrol will be dosed at 6 mg/kg/d at weeks 10-11, at 4 mg/kg/d at week 12, at 2 mg/kg/d at week 13, and fully tapered at the end of week 13.
Duration of administration	4 weeks of Megestrol, 24 weeks of iKanEat behavioral intervention
Reference therapy	Placebo for Megestrol
Statistical Methodology	The outcome measure for Aim 1 is a binary variable indicating whether a child obtains 90% or more caloric intake on oral feeding at the end of the intervention. A chi-square test or Fisher's exact test will be used to compare the rates of oral feeding between the two groups.

CONFIDENTIAL

This material is strictly confidential and is intended solely for the guidance of clinical investigation. Do not disclose or use except as authorized in writing by the study sponsor

1 Introduction

This document is a protocol for a human research study. This study is to be conducted according to US and international standards of Good Clinical Practice (FDA Title 21 part 312 and International Conference on Harmonization guidelines), applicable government regulations and Institutional research policies and procedures.

Feeding problems requiring medical intervention occur in 3-10% of children (1). Premature infants are overrepresented among children with feeding problems (2). Improved preterm infant survival has increased the prevalence of feeding problems in older infants and toddlers (3). In addition, severe feeding problems occur in 40-70% of children with chronic medical conditions (4,5). Neonates with long intensive care hospitalizations may lose opportunities for learning to eat and may associate eating with pain or discomfort (6). Gastrostomy (G-) and gastrojejunal (G-J) tube feeding requirements may persist for months or years resulting in chronic oral food refusal. As the prevalence of gastrostomy tube feeding has increased, so have the challenges associated with managing a child with tube feeding and transitioning a child from tube to oral feeding (7,8). Previous research on transitioning children from tube to oral feeding indicates that most programs are inpatient or intensive day treatment, and many children are not successful (8).

Our team developed a novel interdisciplinary outpatient protocol for transitioning children from tube to oral feeding (9,10) called iKanEat. Data indicate iKanEat is effective for transitioning tube fed children to eating by mouth. iKanEat results in statistically significant and clinically meaningful increases in oral eating. iKanEat is composed of several key components, including two medications – amitriptyline and megestrol. However, our most recent work (HD066629)(11) demonstrated that amitriptyline is not a necessary component of the protocol, as all children who completed the protocol consumed 100% of their calories orally at post treatment regardless of receiving amitriptyline or placebo. The current proposal is a randomized controlled trial of the second medication (megestrol) compared to placebo, to ensure that the addition of a 4-week course of megestrol improves child outcomes within the iKanEat protocol. Because corticosteroids can have significant side effects, it is critical we determine if the benefits of megestrol as part of iKanEat outweigh the risks of the medication.

1.1 Background

Gastrostomy Tube Feeding

Gastrostomy (G-) and gastrojejunal (G-J) feeding tubes are placed in infants and children who refuse to eat or are unable to eat enough to sustain normal growth. Common medical causes of inadequate weight gain include neurological disease, congenital heart defects, chronic pulmonary disease, renal failure, genetic disorders, anatomic abnormalities, behavioral disorders, and oropharyngeal dysphagia (4,19). Although usually intended as temporary, short-term solutions to medical complications, feeding tubes can become a permanent conduit for enteral nutrition.

Although tube feeding routinely saves the lives of children who are unable or unwilling to eat by mouth, chronic tube feeding is a burden to patients, caregivers, and families. First, the decision to have a G-tube placed is difficult for caregivers (20). Once it is placed, caregivers cope with complications including vomiting, diarrhea, infection of the G-tube insertion site, granulation tissue, and leakage of gastric contents (21). Stress levels of caregivers often increase after G-tube placement (22). Because eating is such an integral part of culture, there are many mealtime socialization issues that children and parents miss when the child is tube fed (20). In addition, parents report negative issues secondary to G-tube feeding such as sleep disruption and deprivation, restricted ability to leave the home, childcare problems, negative attitudes of others toward feeding, and difficulties finding a place to feed (21). Although some

CONFIDENTIAL

This material is strictly confidential and is intended solely for the guidance of clinical investigation. Do not disclose or use except as authorized in writing by the study sponsor

studies do find that G-tube placement can improve quality of life for parents in the short term (23), there is consensus that delaying the transition from tube to oral feeding has negative medical, emotional, and economic consequences (21,24).

Transitioning to Oral Feeding

Existing treatment options for transitioning children with severe feeding problems from tube to oral feeding include outpatient, inpatient, and day treatment. The most widely available treatment option for severe feeding problems is outpatient treatment by a multidisciplinary team (25). These teams include professionals from multiple specialties, including pediatric gastroenterology, psychology, speech, occupational therapy, and nutrition (4). Outpatient treatment is typically covered by health insurance, and can be tailored to meet the needs of the patient and family. Typically the patient and family see the providers regularly (i.e., monthly, quarterly) to receive recommendations that are then implemented in the home. Despite the prevalence of outpatient feeding programs, there is little published evidence on outcomes of these programs.

Inpatient programs take place in a hospital setting, and are justified when: 1) a child's feeding problems are leading to severe weight loss; 2) outpatient treatment has proven unsuccessful; and/or 3) parents are willing to participate (increasing the likelihood of generalization to the home setting, (22)) The advantages of inpatient treatment include reduced access to food between meals and the ability of the professionals to feed meals daily (22). These types of inpatient treatment programs are effective at increasing child oral intake and decreasing mealtime behavior problems (23). Yet, there are many drawbacks to inpatient treatment including high cost, large burden on the family, extensive demand on professionals, and difficulties with generalization of treatment gains to the home environment (23).

Day treatment programs have become more common in the last decade. They capitalize upon many of the strengths of an inpatient program mentioned above, but have lower costs (due to the lack of overnight stays). However, cost is still high, and some experts have expressed concern that treatment gains may not generalize to the home environment (24-26).

Therefore, although treatment options do exist for tube fed children, empirically supported inpatient treatment programs are intensive and expensive, and there is little evidence that outpatient programs are effective.

1.2 *Investigational Agent*

Oral Suspension: Each mL of lemon-lime flavored oral suspension contains: megestrol acetate 40 mg. Inactive ingredients: anhydrous citric acid, natural and artificial lemon-lime flavor, polyethylene glycol 1 450, polysorbate 80, purified water, sodium benzoate, sodium citrate dihydrate, sucrose and xanthan gum. Bottles will be stored at room temperature (15 to 30°C). Protect from temperatures above 30°C (41).

The precise mechanism of action by which megestrol produces its antineoplastic effects is unknown at present. Pharmacologic doses of megestrol exerted a direct cytotoxic effect on human breast cancer cells in vitro and proved capable of modifying and abolishing the stimulatory effects of estrogen on breast cancer cell lines. Megestrol may have other mechanisms of action as well, including an antiandrogen activity, suppression of adrenal androgens, and possibly the inhibition of enzymes, e.g., 5 a-reductase, critical to androgen metabolism within the prostate. The precise mechanism of action by which megestrol produces its antianorexic and anticachectic effects is also unknown at present. The gain in weight associated with megestrol is associated with increased appetite, an increase in fat and body cell mass (41).

CONFIDENTIAL

This material is strictly confidential and is intended solely for the guidance of clinical investigation. Do not disclose or use except as authorized in writing by the study sponsor

1.3 Review of Literature

Feeding

Our team has published several studies of pediatric feeding difficulties. Our early work examined the relationship between feeding difficulties and medical complexity (27), and found that by the time of introduction of solid food, preterm children more often demonstrated difficulty than full-term children. Also, medical factors, primarily the need for breathing assistance, accounted for more of the variance in this relationship than prematurity alone. We have also assessed parent perceptions of mealtime behaviors in children who are tube fed, and learned that parents report surprisingly high levels of stress around the mealtime, both for themselves and their children (28). We have also examined pediatric sensory processing issues related to feeding problems (29) and found that 67% of children who present for treatment have sensory profile scores in the abnormal range. Also, co-occurring diagnoses are frequent in the areas of developmental, gastrointestinal, and neurological areas. This foundational work led to the multidisciplinary protocol which we call iKanEat that was designed to move these complicated children to oral eating on an outpatient basis.

Clinical Data: iKanEat

In 2008, our team published a retrospective chart review of the first 9 patients to undergo our iKanEat tube weaning protocol clinically (30). At that time, the protocol included two medications (amitriptyline and megestrol) as well as behavioral and oral motor/sensory components. Results from this initial retrospective study indicated that the nine initial patients were 100% orally fed at the end of the intervention period, and 8 of the 9 were 100% orally fed six months later (one patient with cerebral palsy had stamina issues and was only able to sustain 50% of intake orally over the long term). This pilot work led us to NIH funding to conduct a randomized controlled trial of amitriptyline, one of the two medications in the protocol (HD066629). The findings (11) suggest that 100% of children who completed the protocol moved from tube feeding to total oral feeding, regardless of group assignment (amitriptyline, placebo). More specifically, of the children who completed the 6 month protocol, % kilocalories/day obtained orally (our primary outcome measure) increased statistically significantly from $M = 31.51\%$ ($SD = 16.09\%$) to 100%. Therefore, it does not appear that amitriptyline is a necessary component of the iKanEat protocol.

Parent Stress

During the iKanEat protocol, we expect the child to lose weight during weeks 10-14 as the children taper off the tube. We inform parents of this expected weight loss and monitor the children closely. Despite this, in the previous trial there were instances of parents withdrawing their children during this weight loss period despite the physician guidance that the weight loss was expected and safe. It is critical that we learn more about this stressful period of the iKanEat protocol so we can better help parents through this transition. The current study design will allow us to learn more about how and when parent stress changes throughout the protocol in order to target supplemental treatment efforts related to parent stress.

Quality of Life.

Our most recent study (HD066629) also examined the role of pain and quality of life in tube weaning. Findings demonstrate improvement in pain symptoms ($t = 1.85$, $p = .006$) and in several areas of quality of life (i.e., growth and development, $t = -2.285$, $p < .05$; behavior, $t = -2.376$, $p < .05$; general health perceptions, $t = -2.232$, $p < .05$; parental impact: emotional and time, $t = -3.718$, $p < .005$) in the transition from tube to oral feeding.(11) In the current protocol we will assess whether successful transition to oral feeding has an effect on parent and child quality of life.

Remote Interventions.

CONFIDENTIAL

This material is strictly confidential and is intended solely for the guidance of clinical investigation. Do not disclose or use except as authorized in writing by the study sponsor

Our team has extensive experience delivering multidisciplinary feeding team clinical visits via interactive televideo. These visits are delivered as part of routine feeding team care in our clinic, and include both new patient visits and return patient visits. This clinical experience will serve our team well regarding the current scope of work.

Gut Microbiota

The gut microbiota refers to the species of bacteria living in the gut, and plays an essential role in digestive and immune function. Little is known about the effect formula feeding has on the microbiome, and the effects of transitioning from tube feeds to oral feeding. In the current protocol, we will assess whether successful transition to oral feeding has an effect on the gut microbiota.

Most tube fed children receive a commercial formula through their tube as these formulas are easy to prepare and safe. However, some children do experience gastrointestinal discomfort with tube feeding, and recently, some clinicians and parents have been exploring the use of pureed diets to remedy these issues (e.g. retching, coughing). Very few studies have been conducted examining a blended diet, but Pentuik et al.⁴⁷ studied 33 children receiving a pureed diet by tube. Results indicate that both gagging and retching (73% of patients with 50% reduction in symptoms) improved when children were moved from a formula diet to a pureed diet. A more recent study demonstrated increased microbial diversity in 17 tube fed children, transitioned from commercial formula to a blenderized diet.⁴⁸

Research indicates that both diet^{49, 50} and the introduction of solid foods have an effect on microbiota.⁵¹ In fact, changes in the gut microbiota can be seen as rapidly as 24 hours after dietary changes occur.^{52, 53}

There are no published pediatric studies to date examining the differences in microbiota between children who are tube fed versus fed orally.

Summary

Our previous work suggests that iKanEat is effective in moving children from tube to oral eating, and that amitriptyline does not improve the outcomes associated with the protocol. However, we do not know if the remaining medication (megestrol) improves the outcomes associated with iKanEat. As all medications have risks, it is necessary to test this remaining medication to determine if the risk is outweighed by the benefit the medication brings to the iKanEat protocol.

Rationale

Tube fed children have few treatment options for moving from tube to oral feeding, causing substantial economic impact on their families and the health care system, as well as negatively impacting many parent and child factors including stress and quality of life. Previous research by our team detailed above indicates that iKanEat is an effective weaning protocol when used in combination with megestrol. The current study will provide important information about one of the only empirically supported outpatient treatment protocols for moving children from tube to oral eating, and will also provide much needed information on parent stress and parent and child quality of life during this transition period.

1.4 Dose Rationale and Risk/Benefits

The dose of the megestrol was based upon the preliminary clinical data published.

CONFIDENTIAL

This material is strictly confidential and is intended solely for the guidance of clinical investigation. Do not disclose or use except as authorized in writing by the study sponsor

2 Study Aims

The primary aim of the current study is to conduct a randomized controlled trial of a 4-week course of megestrol, the only remaining medication that is part of the iKanEat protocol, to ensure that the addition of megestrol results in improved child outcomes. The second aim is to assess the safety of megestrol as part of the iKanEat protocol. Our previous work (as well as work by others) suggests that a 6 week course of megestrol can lead to adrenal insufficiency in some children (11-14), so as part of the current protocol, we will assess the safety of a 4 week course of this drug.

Finally, parents of tube fed children encounter multiple psychosocial stressors regarding tube feeding (15). These include concerns about their child's survival due to their underlying medical issues, feelings of "failure" due to their inability to feed their child orally (16), increased feelings of stress around the tube feeding (17) and decreased support from others due to the tube feeding (18,19). Our research indicates that quality of life can be poor in tube fed children (11), even more so than children with cancer or burns. Given the significance of these issues, the third aim of the study is to examine the effect of the transition from tube to oral feeding on parent stress and parent and child quality of life.

Aim 1: To assess the efficacy of megestrol as part of the 24 week iKanEat protocol.

Hypothesis 1: Children randomized to the megestrol group will be significantly more successful in making the transition to oral feeding (defined as obtaining at least 90% of calories orally) than children randomized to the placebo group.

Aim 2: To assess the safety of 4 weeks of megestrol as part of the 24 week iKanEat protocol.

Hypothesis 2A: Children randomized to the megestrol group will not differ from control children in morning cortisol classification level (low, average, high) and will remain within the normal range at all time points.

Analyses 2B: Exploratory analysis will determine which, if any, covariates (gender, age, and diagnoses at week 0, diagnoses at birth) are related to abnormal morning cortisol levels.

Aim 3: To examine the effect of the transition from tube to oral feeding on parent stress and parent and child quality of life. Hypothesis 3A: The transition to oral feeding will temporarily increase parent stress at week 14 at the cessation of tube feeding, with a return to baseline by week 24. Hypothesis 3B: The transition to oral feeding will increase parent/child quality of life at 24 weeks compared to week 0. Children with feeding tubes have few options for treatment other than extensive inpatient stays and expensive day treatment programs. iKanEat offers an outpatient, less intensive, empirically supported effective treatment option that can improve the lives of children and families. It is imperative that we determine the efficacy and safety of the protocol including 4 weeks of megestrol before we move toward broad dissemination of the iKanEat protocol.

Aim 4: To examine the effect of the transition from tube to oral feeding on the gut microbiome. Hypothesis 4A: The transition to oral feeding will increase the variety of food consumed orally, thus diversifying the gut microbiome by week 24. Hypothesis 4B: Children who are on a blended diet formula at week 0 will have a more diverse microbiome than children on commercially prepared formula prior to transitioning to oral feeding (Week 0, 10). Little is known about the gut microbiota of children who transition from formula feeding to oral feeding. Determining the changes in the gut microbiome could add to general knowledge about how the gut microbiome adapts to changes in diet over time in children who transition from commercial or blended formulas to a diet consumed orally.

CONFIDENTIAL

This material is strictly confidential and is intended solely for the guidance of clinical investigation. Do not disclose or use except as authorized in writing by the study sponsor

3 Study Design

3.1 General Design

This is a multi-center, randomized, placebo-controlled, double-blind clinical trial. The primary focus of the study is the evaluation of the effectiveness of treatment with megestrol as part of a 24 week behavioral feeding protocol in transitioning from tube to oral feedings in a pediatric population. Approximately 60 pediatric subjects matching the criteria for eligibility will be enrolled in the study and randomized to receive either megestrol (n=30) or placebo (n=30).

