4.3 Subject Recruitment and Screening

Sixty subjects are needed for our analysis plan, so with a maximum of 20% drop out (which exceeds drop out from our previous work), a total sample of 72 will need to be recruited over the 5 year project (for more information see Sample Size Determination in Data Analysis Plan section). To allow for study start up and completion phases, we will need to recruit approximately 20 subjects per year when in active recruitment. Currently, the University of Kansas Medical Center team sees 12 new patients per month, Children's Mercy Hospital sees 12 new patients per month, University of California San Diego/Rady Children's Hospital sees 8 new patients per month, the New Orleans site sees 8 new patients per month, Arnold Palmer Hospital for Children sees 8 new patients per month, and Children's Hospital of Philadelphia sees 12 new patients per month, resulting in a total potential recruitment base of 60 feeding subjects per month across our primary sites. Based upon clinic data, 20% of the patients seen will meet inclusion/exclusion criteria (resulting in 12/month or 144/year). Of these, we predict that half will be given permission to participate, given the highly medically complex nature of many children with feeding problems (resulting in 72/year). Assuming that half of eligible families participate (36/year), current clinic volume at participating sites will result in successfully meeting recruitment goals.

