7.1 Sample Size Determination and Statistical Methods

For Aim1 (To assess the efficacy of megestrol as part of the 24 week iKanEat protocol), if at least 90% of the treatment group successfully transitions (in pilot 100% successfully transitioned), with 72 participants, we would have .80 power to detect an odds ratio of .21. With 60 participants, we would have power to detect an odds ratio of .18. If only 75% of the treatment group successfully transitions, we will still have .80 power to detect an odds ratio of .25 with our smallest expected sample size of 60.

For Aim 2 (To assess the safety of megestrol as part of the 24 week iKanEat protocol), all analyses are descriptive, so a power analysis is not conducted.

For Aim 3 (To examine the effect of the transition from tube to oral feeding on parent stress and parent and child quality of life), with 60 participants, we would have .78 power to detect differences in slopes over the four data points equivalent to a standardized effect size of $d=.75$ or larger. With a sample size of 72, there will be .80 power to detect a difference in slopes equivalent to a standardized effect size of .70. To answer those questions in which the grouping factor is success in treatment, such as 3A (The transition to oral feeding will temporarily increase parent stress at week 14 at the cessation of tube feeding, with a return to baseline by week 24) and 3B (The transition to oral feeding will increase parent/child quality of life at 24 weeks compared to week 0), assuming that 60% of the participants across groups are successful, we would have sufficient power to detect effects equivalent to a standardized effect size of $d=.42$ or larger. With a sample size of 60, the minimum detectable effect size would increase to $d=.59$. If 70% percent are successful, with 72 participants we can detect effects equivalent to $d=.61$, and with 60 participants $d=.70$. These are moderate sized effects.

Planned Analyses

CONFIDENTIAL

This material is strictly confidential and is intended solely for the guidance of clinical investigation. Do not disclose or use except as authorized in writing by the study sponsor

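### Section 3.1 randomizes about 60 children, but 4.3 and 7.1 treat 60 as the number left for analysis out of 72 recruited; the plan needs one stated randomization target

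*Combined protocol and SAP*

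**What the plan says.** The figure 60 appears in four places and does not always mean the same thing.

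- **Study Summary (synopsis):** "Number of Subjects 60". No arm split is given, and nothing says whether the children are recruited, randomized or analysed.
- **3.1 General Design:** "Approximately 60 pediatric subjects matching the criteria for eligibility will be enrolled in the study and randomized", and the sentence goes on to fix the arms: "randomized to receive either megestrol (n=30) or placebo (n=30". Here 60 is the number entering the trial.
- **4.3 Subject Recruitment and Screening:** "Sixty subjects are needed for our analysis plan, so with a maximum of 20% drop out", and therefore "a total sample of 72 will need to be recruited over the 5 year project". Here 60 is the number left after dropout.
- **7.1 Sample Size Determination and Statistical Methods:** detectable effects for Aims 1 and 3 are given at both 72 and 60 participants, and the lower figure is described as "our smallest expected sample size of 60".

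Three other provisions bear on the point. Section 6.2 randomizes children once the Week 0 visit is complete, and 5.3 allocates them 1:1 within site. Section 4.4.2 asks withdrawn families to continue with assessments. The analysis populations paragraph in section 7 makes the protocol-compliant population primary and the all-treated population secondary.

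**The concern.** Section 3.1 states the number to be randomized, and that number equals the one 4.3 says must survive dropout. Both cannot describe the same trial unless nobody is lost. Under 3.1, 60 is about the largest sample the analysis could have. Under 7.1 it is the smallest expected.

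At stake is which sample the stated power refers to. If 60 are randomized, the figures given for 72 participants describe a trial that will not exist. Those given for 60 hold only with complete retention in the primary population. Dropout after randomization is a realistic prospect: allocation is at Week 0, study drug starts at Week 10, and the outcome is at Week 24. Section 1.3 (Parent Stress) records that parents in the previous trial withdrew children during the weight-loss period.

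**Working it through.** **Inputs.** 60 randomized, 30 per arm (3.1); 60 needed for analysis, dropout at most 20%, 72 recruited (4.3); for Aim 1 at 60 participants, an odds ratio of .18 from a 90% treatment-group success rate and .25 from 75% (7.1); 1:1 allocation (5.3). Alpha and sidedness are not stated, so two-sided 5% is assumed below.

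**Step 1: reproduce the plan's 72.** 60 × (1 + 0.20) = 72, which matches exactly. So 4.3 takes 60 as the post-dropout number and adds the allowance on top. The gap of 12 between 3.1 and 4.3 is exactly that allowance.

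**Step 2: what remains if 60 are randomized.** At the ceiling, 60 × (1 − 0.20) = 48, or 24 per arm, 12 below the stated need. Using the plan's own ratio instead, 60 / 1.2 = 50. With any loss above zero the result is below 60.

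**Step 3: precision.** Standard errors scale with 1/√n, so intervals widen by √(60/48) = 1.12.

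**Step 4: power.** The control rate follows from control odds = OR × p/(1 − p), where p is the treatment-group rate.

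- 90%, OR .18: odds = 9 × .18 = 1.62; rate = 1.62/2.62 = 61.8%.
- 75%, OR .25: odds = 3 × .25 = 0.75; rate = 0.75/1.75 = 42.9%.

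Power of the uncorrected two-sided 5% chi-square test, by summing binomial probabilities over all tables that reject:

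| Effect | 36 per arm (72) | 30 per arm (60) | 24 per arm (48) |
|---|---|---|---|
| 90% vs 61.8% (OR .18) | .825 | .751 | .666 |
| 75% vs 42.9% (OR .25) | .803 | .730 | .654 |

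From 60 to 48 the loss is .751 − .666 = .085 and .730 − .654 = .076, about 8 points. The pooled normal approximation gives a similar picture: .734 to .633 and .727 to .626, about 10 points.

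At 60 this test gives .75 and .73, not .80. That part of the shortfall is already there at 60 analysed and has nothing to do with the enrolment figure. Only the further fall belongs to this point.

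**Step 5: check the obvious repair.** If 72 are randomized and 20% drop out, 72 × 0.80 = 57.6 remain, about 58. Holding 60 at 20% loss would need 60/0.80 = 75. So naming 72 in 3.1 removes the contradiction but does not make 60 a guaranteed floor.

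**The case against.** The best case for the plan is that 4.3 is the section on recruitment, gives 72 as the operative number and points to the sample-size section, while 7.1 carries 72 through. On that reading 72 governs, and the sentence in 3.1, which opens with an approximation, loosely describes the analysed number. This is plausible. It means the power loss is conditional on someone acting on 3.1. It does not remove the conflict: 3.1 says the 60 are randomized and gives 30 per arm, and 72 is 20% above 60, more than an approximation covers.

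A second defence is that 72 are recruited and 60 of them randomized. That fails because 7.1 computes power for 72 participants.

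A third is that losses will be smaller, or recovered. Section 4.3 does say that 20% exceeds dropout in earlier work, so 48 is the bottom of the planning range. Section 4.4.2 does seek outcomes from withdrawn children, so the secondary all-treated analysis could hold more than 48. But the primary population is protocol-compliant, and follow-up does not restore children without the required drug exposure and procedures.

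Two stronger readings are tempting and should be resisted. A reader might infer that the synopsis also randomizes 60, 30 per arm; it gives only the number and is compatible with 60 analysed. A reader might also infer that randomization lists or site quotas are set from 3.1. The documents do not say so: 5.3 gives no list length, and no site quotas are stated.

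**Conclusion.** The inconsistency is real and stands as written in 3.1 against 4.3 and 7.1. The synopsis is ambiguous rather than contradictory.

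Its size depends on which figure is followed. If 72 are randomized, the harm is confined to an incorrect sentence in 3.1. If randomization stops at 60, the primary analysis falls below the stated need with any dropout. At the 20% ceiling it holds 48, with intervals about 12% wider and power about 8 points lower for the effects quoted at 60. Those power figures assume a two-sided 5% chi-square test, equal arms and equal dropout. The synopsis names a chi-square or Fisher's exact test, but the planned analysis in section 7 is a logistic model with site effects, so they illustrate the loss and do not predict the model's power.

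A reader might infer that the trial will analyse 48 children, or that the whole gap to .80 comes from this discrepancy. Neither is supported: 48 is conditional on stopping at 60 and on maximum dropout, and part of the gap is present at 60 analysed.

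**What to change.** State one number to be randomized, identically labelled, in the synopsis, 3.1, 4.3 and 7.1. In 3.1, replace 60 (30 per arm) with the recruitment figure of 4.3, which as written is 72 (36 per arm), and label 60 everywhere as the number needed for analysis. In the synopsis, say which of the two numbers is meant.

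Do not describe 60 as the guaranteed minimum unless the target agrees with the dropout allowance, since 72 at 20% loss leaves about 58.

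If 60 randomized is the true cap, keep 3.1, correct 4.3, and restate the Aim 1 and Aim 3 figures in 7.1 for the number left after dropout, about 48 at 20%.

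The cost is wording only. The first route adds no children beyond those 4.3 already plans to recruit; the second accepts less favourable stated power.
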